**[name], [name], [name], [name], [name], [name], [name], [name], [name], [name], [name], [name]**

**Primary Aim** of this proposal is to demonstrate that tranexamic acid (TXA) reduces intraoperative blood loss and transfusion requirements during and following posterior lumbar spinal fusions

**Primary Hypothesis:**

TXA reduces intraoperative and postoperative (up to 7 days) blood loss and transfusion requirements.

**Primary Objective:**

1. To test the effect of TXA on the need for red blood cell (RBC) transfusion (intraoperatively and postoperatively) in patients undergoing lumbar spinal fusion compared to placebo (Normal Saline). This will be adjusted for number of levels to fuse, duration of surgery and patient's weight.
2. To test the effect of TXA on blood loss adjusted for weight, duration and number of level fused

**Secondary Objectives:**

1. To test the effect of TXA on the following:
  - a. Duration of surgery (Skin to skin)
  - b. Length of hospitalization (LOH)
  - c. Cost/effectiveness analysis
2. To assess the safety of TXA.

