**Protocol:**

## PROTOCOL

Patients of ages 18 to 90 years old with ASA class I-IV undergoing elective lumbar interbody fusion (PLIF or TLIF) for degenerative disc disease (DDD) are considered eligible for inclusion in this study. Patients are screened for the inclusion/exclusion criteria below. Patients will enroll

in the study at the time of signing consent for surgery at their preoperative visit. Participation in the study has no bearing on their consent for surgery. After the patient signs consent at the preoperative visit, they will complete the baseline cognitive assessment (TICS-m, COWAT, TMT, BDI, 3D-CAM). Patients will have from the first visit until the day of surgery to withdraw from the study (2-6 weeks) and from the first visit to the preop visit to consent (1-4 weeks). Once patients are consented, they are considered enrolled. Patients can withdraw out of the study at any time prior to surgery. Once they withdraw, they will no longer be considered participants in the study. Patients will be randomized (blind randomization) using SPSS to placebo vs TXA. The primary surgeon, anesthesia care provider, investigator, and outcomes assessor will be blinded to the treatment and control arms. The intraoperative estimated blood loss in milliliters will be recorded routinely by the anesthesiologist participating in the case. All patients will be discharged to the neurosurgical or orthopedics wards postoperatively. Twice daily (~8am and ~4pm) a study member will administer the 3D-CAM or CAM-ICU delirium screening assessments to determine delirium status. Patients are followed until their second postoperative visit to clinic, approximately 3 months after the surgery. At the first visit, patients will be screened for any adverse events. At both the first and second visit postoperatively, the patients will complete the cognitive testing (TICS-m, COWAT, TMT, BDI, 3D-CAM).

Baseline Demographics/Data	
Age	Chronic Liver Disease
Sex	History of DVT, PE, TEE
Height	Oral anticoagulation (and reason for it)
Weight	Oral antiplatelet therapy (and reason for it)
BMI	Visual impairment
Smoking (Yes/No)	Number of levels fused
DM	Number of Interbody fused
Coronary Artery Disease	ASA classification
Peripheral Vascular Disease	OB/GYN: breast feeding, OCP or pregnant

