### **Sample size calculation for Secondary endpoints:**

1. We do not anticipate any difference in thrombosis complications as a meta-analysis showed an OR of 0.99 (95% CI: 0.06 to 16.07).
2. Analyses for LOH will be based on the difference in mean hospital stay between the 2 groups. This will be adjusted on the number of level fused, presence of a neurological deficit, and BMI
3. Cost effectiveness analysis: The cost of TXA has to be compared with the cost reduction from shorter LOH and reduction in transfusion requirements.

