#### **Analysis of Secondary End Points:**

1. LOH: LOH will be defined from the day of surgery until the patient is medically ready for discharge. The 'actual LOH' will be defined as the duration from the day of surgery to actual discharge. The discharge will depend on the patient insurance and facility availability. The 'actual LOH' will reflect the duration of hospitalization in the general community, while the LOH will reflect the effect of TXA on improving the postoperative course of the patient. We will test for difference in mean between the 2 groups for both LOH and 'actual LOH'. A multivariable linear regression model will be used to adjust for factors related to longer LOH such as BMI, higher ASA score preoperatively, SF-36/PROMIS, and number of level fused.
2. We will analyze the cost-effectiveness of TXA by computing the cost reduction from the decreased in transfusion and LOH and the cost increase from treating TXA related side-effects: additional thromboembolic complications (cost of diagnosis and treatment). We will test for the difference in the mean between the two groups.
3. The other endpoints (cognitive assessments) are exploratory.

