Cover Page for Statistical Analysis Plan

Sponsor-Investigator:	[name]
NCT Number:	NCT04272606
Unique Protocol ID:	201912099
Official Title:	Prospective, Randomized, Double Blind Study on the Effects of Tranexamic Acid on Intraoperative Blood Loss During Lumbar Spinal Fusion And Instrumentation
Date of Document:	05 December 2023

Statistical Analysis

All analyses will be conducted using R statistical software (version 4.3.1). Continuous variables will be summarized using medians and interquartile ranges and comparisons between groups will be done made using Wilcoxon rank sum or Kruskal-Wallis tests. Pairwise analyses within a group will be made using the Wilcoxon signed rank test. Categorical variables will be summarized using counts and percentages, and comparisons between groups will be performed using Pearson χ^2 test or Fisher exact test. Kendall's tau (τ) will be used as a non-parametric test of association between variables. For all analyses, the threshold for significance will be <0.05 without adjustment for multiple comparisons. Variables will be compared between groups by calculating standardized mean differences.

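### Duration of surgery, a secondary objective, has no analysis of its own; adjusting for planned number of levels could gain precision at almost no cost

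*Protocol*

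**What the plan says.** Protocol, Secondary Objectives, item 1a, names "Duration of surgery (Skin to skin") as an outcome on which the effect of TXA will be tested. Duration appears again in the protocol's outcome assessment, under clinical efficacy evaluation. It is not in the list of secondary endpoints, which holds safety, length of hospitalization (LOH) and cost effectiveness. Neither the section on sample size for secondary endpoints nor Analysis of Secondary End Points gives it an analysis.

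The SAP has one rule for all continuous variables: "comparisons between groups will be done made using Wilcoxon rank sum or Kruskal-Wallis tests". It names no covariate for any outcome, and "the threshold for significance will be <0.05 without adjustment for multiple comparisons".

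Elsewhere the protocol intends to adjust for the number of levels:

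- Transfusion (Primary Objective, item 1): "This will be adjusted for number of levels to fuse, duration of surgery and patient's weight".
- Blood loss (Primary Objective, item 2): "To test the effect of TXA on blood loss adjusted for weight, duration and number of level fused".
- LOH (Sample size calculation for Secondary endpoints, item 2): "This will be adjusted on the number of level fused, presence of a neurological deficit, and BMI". Analysis of Secondary End Points, item 1, adds: "A multivariable linear regression model will be used to adjust for factors related to longer LOH", with levels among those factors.

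The baseline data table includes "Number of levels fused".

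**The concern.** By default, duration gets a two-group rank test with no covariates. An operation on more segments can be expected to take longer. If it does, the variation between patients in the size of the operation stays in the error term, and the comparison is less precise than the same 100 patients could give. The section on randomization describes variable blocks and mentions no stratification by levels, so the design does not remove this variation either.

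Duration also differs from the other outcomes in one respect. Bringing the protocol's own adjustments into the SAP would cover transfusion, blood loss and LOH. It would not cover duration, because the protocol gives no adjusted analysis of it. At stake is the efficiency and clarity of one secondary comparison, not the validity of the trial.

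**Working it through.** **Plan's own figure.** The documents give no SD, target difference or power for duration, so there is nothing to reproduce. The stated sample size (40 evaluable and 50 recruited per group, 90% power) concerns blood loss and transfusion only.

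**Inputs.**

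- From the protocol: 50 per arm, 1:1 allocation.
- From the SAP: significance threshold 0.05, taken here as two-sided because sidedness is not stated.
- Assumed: R-squared, the share of variance in log duration explained by levels, from 0 to 0.5; total SD of log duration 0.35; a true shortening of 15% or 10%; in the simulation, 1, 2, 3 and 4 levels in 45%, 35%, 15% and 5% of patients.

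**Step 1: standard error.** In SD units the unadjusted standard error is √(2/50) = 0.200. Adjustment multiplies it by √(1 − R²). The unadjusted trial of equal precision has 100/(1 − R²) patients.

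| Assumed R² | SE multiplier | Cut in SE | Equivalent unadjusted N |
|---|---|---|---|
| 0 | 1.00 | 0% | 100 |
| 0.1 | 0.95 | 5% | 111 |
| 0.2 | 0.89 | 11% | 125 |
| 0.3 | 0.84 | 16% | 143 |
| 0.5 | 0.71 | 29% | 200 |

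**Step 2: power for a 15% shorter operation.** On the log scale the effect is −ln(0.85) = 0.1625, or 0.1625/0.35 = 0.464 SD. For the rank-sum test, with its efficiency of 0.955 relative to the t test under normality, power ≈ Φ(0.464 × √0.955/0.200 − 1.96) = 62%. For the adjusted model, power ≈ Φ(0.464/(0.200 × √(1 − R²)) − 1.96). Simulation with 4,000 runs per scenario gives slightly lower values, and these are the ones used here.

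| Analysis | Formula | Simulation |
|---|---|---|
| Rank-sum, unadjusted | 62% | about 61% |
| Adjusted, R² = 0.1 | 69% | 67% |
| Adjusted, R² = 0.2 | 74% | 73% |
| Adjusted, R² = 0.3 | 79% | 77% |
| Adjusted, R² = 0.5 | 91% | about 90% |

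**Step 3: power for a 10% shorter operation.** In the same simulation the rank-sum test has about 31%. The adjusted model has about 35%, 39%, 43% and 55% at R² = 0.1, 0.2, 0.3 and 0.5.

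**Step 4: type I error.** With no treatment effect, both methods rejected in about 5% to 6% of simulated trials. The gain in power does not come from extra false positives.

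**The case against.** The strongest reply is that the central premise is not in the documents. A reader might infer that number of levels drives duration and that the plan therefore certainly wastes precision. No section says how strongly the two are related. At R-squared 0 nothing is gained, and at 0.1 only 5% of the standard error. This stands, and the point is conditional for that reason.

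A reader might also infer that a real shortening would probably be missed. The figures do not bear that out. Under the stated assumptions the rank-sum test detects a 15% shortening about 61% of the time. For a 10% shortening even the adjusted model stays below 50% at R-squared 0.3.

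Nor is the rank test biased. Under 1:1 randomization it is valid, and chance imbalance in levels is part of the sampling variation that it already allows for. No design target for duration exists to be missed.

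The contrast with the other outcomes is also less sharp than it looks. The SAP adjusts nothing. The protocol's own primary analysis is an ANOVA in which levels enter only an exploratory interaction model. Only LOH has an adjusted model in the analysis sections. Duration is thus one instance of a wider gap, though one that carrying over the protocol's adjustments would not close.

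Finally, the baseline table's wording can be read as levels actually fused, which is known only after surgery. This stands too, so the fix must name planned levels.

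**Conclusion.** The point holds as a low-cost improvement in efficiency and specification. Duration is a stated secondary objective without an endpoint entry or a named analysis, and the test that applies by default is valid but uses no covariate. Adjusting for planned levels would remove between 0% and 29% of the standard error over R-squared 0 to 0.5. At the upper end that is worth 100 further patients in an unadjusted comparison.

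All of these sizes rest on the assumed R-squared. The power figures also rest on the assumed log SD, mix of levels and effect size. The documents confirm none of them. They do not support a claim of bias, of inflated error or of breached power.

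**What to change.** 1. Add skin-to-skin duration to the protocol's secondary endpoints and name its analysis in the SAP.
2. Analyse log minutes by a linear model with arm and the number of levels planned before surgery. Report the ratio of geometric means with its 95% CI.
3. Define the covariate as the planned number, which the first primary objective already refers to, and record it before incision. Do not use levels actually fused, or anything else recorded after incision. If the baseline field now holds levels actually fused, recover the planned number from preoperative records.
4. Keep the rank-sum test as a sensitivity analysis.
5. If unblinded data have already been seen, label the adjusted model as added later.

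The cost is SAP wording, one degree of freedom, a log-scale model assumption and a check that planned levels are on record. No further patients or visits are needed. If levels turn out to explain little, almost nothing is lost.

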**Exploratory objectives:**

1. To test the effect of TXA on the required duration of subcutaneous drain placement (Hemovac)
2. To assess the effect of TXA on incidence of postoperative delirium.

**Study Design:**

Phase 2B randomized, single-center, double-blinded, placebo vs. TXA clinical trial with 1:1 randomization.

**Primary endpoints:**

1. The amount of RBC transfusion intraoperatively
2. The amount of RBC transfusion up to 7 days postoperatively
3. Measurement of intraoperative blood loss, postoperative blood loss, and total blood loss.

**Secondary endpoints:**

1. Safety analysis: thromboembolic events and worsening renal function in TXA vs placebo
2. LOH

3. Cost effectiveness analysis: cost saving from reduction in transfusion and LOH vs. cost of TXA administration

**Exploratory endpoints:**

1. Duration of drain in place
2. Postop wound complication incidence
3. Incidence of postoperative delirium based on CAM-3D and CAM-ICU delirium screening tools.
4. Effect of delirium on cognitive function.

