**Inclusion Criteria**

- 1) Age 18-90 years
- 2) ASIA anesthesia risk of I to IV
- 3) Patients undergoing posterior lumbar spinal fusion for DDD.
- 4) Patients have failed conservative management, which include PT/OT and/or injections.

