### 3) cognitive evaluations

- CAM-ICU/3D-CAM & 3D-CAM-S will be collected preop, during the hospitalization, and 6 weeks and 3 month follow-up
- TICS-m, TMT, COWAT, and BDI preop, 6 weeks and 3 month follow-up.

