### **Study design:**

**Measures to minimize bias: randomization and blinding:** Randomized block design with variable block sizes will be used to randomize subjects to the 2 groups with a 1:1 ratio. Randomization will be generated by a randomization coding software (SAS Version 9.4). Randomization schema will be distributed to the pharmacy and sequence numbers will be identified to match patient enrollment. We will use triple masking: Concealment of randomization, blinding of treatment (placebo and TXA are indiscernible) and blinding of data analysis. Unmasking will be performed at the end of the trial. We will allow for unplanned masking in case of severe adverse events by the DSMB. (See Adverse events section).

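### Exploratory endpoint 4 compares delirious with non-delirious patients, who are not randomised groups, but the plan names no covariate-adjusted method, so age and preoperative cognition may be read as a delirium effect

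*Protocol*

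**What the plan says.** The fourth item under Exploratory endpoints in the Protocol is "Effect of delirium on cognitive function". The exposure is delirium status, which is found by screening twice a day in hospital: "a study member will administer the 3D-CAM or CAM-ICU delirium screening assessments to determine delirium status". What is randomised is the study drug: "Randomized block design with variable block sizes will be used to randomize subjects to the 2 groups with a 1:1 ratio".

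The cognitive outcomes are scheduled under Outcome assessment, item 3: "TICS-m, TMT, COWAT, and BDI preop, 6 weeks and 3 month follow-up". Age is recorded at baseline, and the entry range is wide: "Age 18-90 years".

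For continuous variables the SAP says that "comparisons between groups will be done made using Wilcoxon rank sum or Kruskal-Wallis tests". It adds that "Pairwise analyses within a group will be made using the Wilcoxon signed rank test", and that Kendall's tau "will be used as a non-parametric test of association between variables". It also lists chi-square or Fisher tests for categorical variables, and standardized mean differences between groups. It assigns no test to any particular endpoint.

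In the Protocol, covariate-adjusted regression is described for length of hospitalization, and a GLM ANOVA for interactions in blood loss. The analysis sections say of the cognitive assessments only that they are exploratory.

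**The concern.** The endpoint is worded causally, but the groups form themselves. Patients who become delirious may be older, or may have scored worse before surgery. Either difference would carry through to 6 weeks and 3 months even if delirium did nothing. None of the SAP's methods has a place for age, preoperative score or treatment arm, although all three are on record. Arm belongs in the list because the Protocol's second exploratory objective asks whether TXA changes the incidence of delirium.

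The open choice between follow-up score and change from baseline adds to the problem. The two carry confounding in different ways and can point in opposite directions, so a choice made after seeing the data could decide whether delirium looks harmful. The SAP applies its 0.05 threshold to all analyses without multiplicity adjustment, so this contrast would yield nominally significant results like any other.

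**Working it through.** The plan gives no figure for this endpoint, so there is nothing to reproduce. The check has two parts.

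**1. Is there an adjusted method anywhere?**

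| Method named | Where | Compares delirious with non-delirious? | Adjusts for covariates? |
|---|---|---|---|
| Rank-sum, Kruskal-Wallis | SAP | Yes | No |
| Signed-rank within a group | SAP | No | Uses own baseline only |
| Chi-square, Fisher | SAP | Yes, for categories | No |
| Kendall's tau | SAP | As an association | No partial form named |
| Standardized mean differences | SAP | Describes imbalance | No |
| Multivariable regression | Protocol, length of hospitalization | Not for this endpoint | Yes |
| GLM ANOVA | Protocol, blood loss | Not for this endpoint | Subgroup interactions |

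No adjusted method is assigned to endpoint 4.

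**2. How much could it matter?**

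Input from the Protocol: 50 recruited per arm and 10% loss, so 2 × 50 × 0.9 = 90 patients. All else is assumed: delirium in 10-20% (90 × 0.10 = 9 to 90 × 0.20 = 18 patients), preoperative gap d = 0.5-0.8 SD (delirious patients worse), pre/post correlation r = 0.6-0.8, scores oriented so that higher is better, two-sided 0.05. The true delirium effect is zero throughout.

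*Model A: follow-up depends on the measured baseline.* Follow-up = r × baseline + noise. Expected differences, delirious minus non-delirious:

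- Follow-up score: −r × d, from −0.6 × 0.5 = −0.30 to −0.8 × 0.8 = −0.64 SD.
- Change: (1 − r) × d, from 0.2 × 0.5 = +0.10 to 0.4 × 0.8 = +0.32 SD. The sign reverses.
- Regression coefficient with baseline in the model: 0.

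*Model B: a stable trait measured with error.* The groups differ by d on the trait at both times, and each test adds error.

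- Follow-up score: −d, from −0.50 to −0.80 SD.
- Change: 0.
- Regression coefficient with baseline in the model: −d + r × d = −(1 − r) × d, from −0.10 to −0.32 SD.

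Simulated rejection rates:

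| Analysis | Model A | Model B |
|---|---|---|
| Rank-sum, follow-up score | about 12-64% | about 26-83% |
| Rank-sum, change | about 6-25% | about 4-5% |
| Regression with baseline score | about 4.6-5.7% | about 8-29% |

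At d = 0.2 SD in Model A, the rank-sum test on follow-up scores rejects in only about 6-9%.

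*Adding age.* A separate set of runs used r = 0.7, delirium in 5-20%, the same gap d in age and in baseline score, and an age coefficient of 0 or −0.2. The rank-sum test on follow-up scores rejected in about 4-5% at d = 0, 8-16% at d = 0.3, 11-34% at d = 0.5 and 23-73% at d = 0.8. Regression with baseline score and age rejected in 4-6%. At d = 0.5, an age coefficient of −0.2 moves the spurious difference in follow-up score from −0.7 × 0.5 = −0.35 to −0.35 − 0.2 × 0.5 = −0.45 SD. Treatment arm was not in any of these runs.

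**The case against.** The case against has real force.

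- **The SAP is not confined to rank-sum tests on follow-up scores.** It includes a paired test within groups, so use of each patient's own baseline is foreseen, and it may intend change scores. That stands, and it is why the 12-64% is conditional on one reading. But the paired test makes no contrast between delirious and non-delirious patients. A significant change in one group and not in the other would not supply one, least of all with 9 against 81 patients.
- **Standardized mean differences would show an imbalance** if applied to the delirium groups. They would show it but not remove it.
- **The gap is assumed.** The documents give neither the incidence of delirium nor the difference between the groups. The exclusions (inability to consent, stroke, intracranial bleeding, seizure disorder, severe cardiac or pulmonary disease, emergent cases) may narrow it. So confounding may occur but is not shown to be certain.
- **Regression does not guarantee 5% error.** A reader might infer from the Model A column that adjustment settles the matter. That result follows from how Model A generates the data. Under Model B the regression is biased and the change score is not.
- **The endpoint is exploratory.** It has no counterpart among the exploratory objectives, and with few cases no method will be precise. This limits the weight of the point, but the wording still claims an effect.

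**Conclusion.** The point holds in a limited form. Endpoint 4 is a non-randomised contrast, no covariate-adjusted method is named for it, and the choice between follow-up and change score is left open. Confounding by age and preoperative cognition may therefore pass as a delirium effect. Under the assumptions stated, false-positive rates run from little above nominal at a gap of 0.2 SD to about 64% in Model A at a gap of 0.8 SD. Both size and sign depend on which score is tested.

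Three stronger readings are not supported. A spurious delirium effect is not bound to appear, because the documents do not show that the groups will differ. The SAP's toolkit is not rank tests alone, although nothing in it adjusts. And the comparison of TXA with placebo is not weakened: it is protected by randomisation, and no primary, secondary or safety conclusion rests on this endpoint.

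**What to change.** In the SAP, for endpoint 4:

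1. For each of TICS-m, TMT, COWAT and BDI at 6 weeks and 3 months, fit a linear regression of the follow-up score on delirium status, with the preoperative score, age and treatment arm as covariates. Name this as the main analysis.
2. Report the delirium coefficient with a 95% CI and call it an adjusted association, not an effect.
3. Add a change-from-baseline analysis as a sensitivity analysis, because error in the preoperative score leaves residual confounding in the regression. If the two disagree, say so.
4. Keep the unadjusted comparison as descriptive.

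The cost is SAP wording and 4 × 2 = 8 short models, each with a sensitivity analysis. All covariates are already collected, and no visit or patient is added. With perhaps 9 to 18 delirious patients under the assumed incidence, the covariates should stop at these three, and the intervals will be wide.
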